## VIII. Gender/Minority/Pediatric Inclusion for Research

### **VIII.1 Inclusion of Women and Minorities**

Inclusion of Women and Minorities: According to U.S. Census Data, 51.3% of Columbus, OH residents are female. In our previous studies with smokers, 55-62% of participants were female. According to U.S. Census data, the racial composition of individuals living in Columbus is 61% White, 28% Black or African American, 5% Asian, 0.2% American Indian/Alaska Native, 0% Native Hawaiian/Other Pacific Islander, and 4% two or more races. The ethnic composition of individuals living in Columbus is 6% Hispanic/Latino. We expect that our distributions will be similar to these but we may potentially have a larger distribution of ethnic and racial minorities, based on our previous studies. However, we will continuously monitor enrollment in order to ensure that we are meeting recruitment goals to avoid under-recruiting minorities. If the targeted enrollment for minorities is not met because they do not respond to the advertisements, we will make special efforts to solicit their participation by advertising in community newspapers, local church organizations, and community centers.

### **VIII.2 Inclusion of Children**

This study will be restricted to individuals 21 years of age and older, which is the legal age to purchase tobacco products.

## **IX. Data and Safety Monitoring Plan**

The Data and Safety Monitoring Plan can be found in Appendix D to this Research Protocol.

All data and safety monitoring will adhere to the policies and procedures of the OSU Comprehensive Cancer Center's Data and Safety Monitoring Plan which has been approved by the National Cancer Institute

## Appendix A: Construction and Verification of the Dual-Hose Research-Grade Waterpipe (RWP2) and Single-Hose Research-Grade Waterpipe (RWP)

[figure not shown]
## Dual-Hose Research-Grade Waterpipe (RWP2)

### RWP2 Construction

The RWP2, pictured in Figure A-1, is constructed from the same materials as the single-hose research-grade waterpipe (RWP) we developed and validated previously. Briefly, all wetted materials have inert surfaces to reduce contamination, guard against memory effects and degradation over time, and facilitate easy cleaning between smoking sessions.

Modifications that were made to the RWP to create the dual-hose RWP2 included changes to the cap design and the addition of a second hose, as shown in Figure 1. Both hoses are equipped with inline topography systems consisting of polycarbonate pneumotachometers (2 total) that are connected to an amplifier as described previously. Two sets of pressure transducers inside the amplifier convert the pressure drop across the restriction inside each pneumotachometer to an electrical response. These data are now recorded electronically for each hose using LabView 2017. Data files are processed manually or automatically in batches using the same algorithm for peak recognition and analysis (MatLab R2018a). The result is a spreadsheet report that describes the volume, duration, average and peak flow rates of each puff, and interpuff intervals for each of the two participants smoking the RWP2.

To increase ruggedness, the design of the neck of the glass flask was changed to eliminate the force associated with the cap's o-ring seal against the inside of the neck. Because the flasks are now being manufactured (by Kimax) with

**Figure A-1. Photo showing the main components of the dual-hose research-grade waterpipe (RWP2); data acquisition system not shown.**

Figure A-2. The neck of the RWP2 was modified with a thicker upper lip and clamp to create a safer seal with the cap, given the manufacturer has reduced the flask's wall thickness.

thinner walls, the neck could no longer safely support the old design. The new design includes a thicker mouth on the flask which supports the weight of the cap. The cap is now sealed to the top of the mouth of the flask using an o-ring and a clamp, as shown in Figure A-2. The dimensions and materials of the head, body, and one-way valve of the RWP2 are unchanged from the original RWP.

### Topography Data Collection and Analysis

The RWP2 has an inline topography system that allows real-time

measurement and recording of the flow rate of smoke drawn through each of the two hoses. This allows the separate measurement and reporting of two individual's puffing behaviors (puff volume, duration, flow rate, and interpuff interval) when smoking a single, shared waterpipe in our controlled clinical research facility. The pneumotachometers introduce minimal draw resistance to the waterpipe (<5% at 27 L/min), and perform reliably, with known precision and accuracy, when measuring flows of waterpipe tobacco smoke.

As with the RWP, the relationship between pneumotachometer response and flow through hoses 1 and 2 of the RWP2 is best described using a quadratic curve fit, as shown in Figure A-3. These data agree well with what was previously reported for the RWP. To simulate normal waterpipe "smoking etiquette," these data were collected in series, first for Hose #1 while Hose #2 was plugged, then for Hose #2 while Hose #1 was plugged. As with all commercial dual-hose waterpipes, smokers of the RWP2 must put their thumb over their mouthpiece when the other person is puffing, otherwise the person will only be sucking in room air. Study participants will be reminded to follow normal waterpipe "smoking etiquette," during the clinic smoking sessions:

- Do not puff at the same time as your partner.
- Unless you are in the act of puffing, plug your hose end with your thumb so that your partner isn't just sucking air from their hose.
- Do not blow or exhale into your hose.

[figure not shown]

Figure A-3. Relationship between flow rate through each hose of the dual-hose research-grade waterpipe and the topography measurement device response.

## Single-Hose Research-Grade Waterpipe (RWP)

### RWP Construction

The RWP, pictured in Figure A-4, was developed and validated previously. Briefly, all wetted materials have inert surfaces to reduce contamination, guard against memory effects and degradation over time, and facilitate easy cleaning between smoking sessions.

For this study, modifications were made to the RWP including the use of new data acquisition hardware and software, and a change to how the cap seals to the flask, as shown in Figures A-4 and A-5. The hose is equipped with an inline topography system consisting of a polycarbonate pneumotachometer that is connected to an amplifier as described previously. The amplifier can take inputs from two separate RWPs. Two sets of pressure transducers inside the amplifier convert the pressure drop across the restriction inside the pneumotachometer to an electrical response. These data are now recorded electronically for each RWP using LabView 2017. Data files are processed manually or automatically in batches using the same algorithm for peak recognition and analysis (MatLab R2018a). The result is a spreadsheet report that describes the volume, duration, average and peak flow rates of each puff, and interpuff intervals for each of the two participants separately smoking their own RWP.

To increase ruggedness, the design of the neck of the glass flask was changed to eliminate the force associated with the cap's o-ring seal against the inside of the neck. Because the flasks are now

[figure not shown]

Figure A-4. Photo showing the main components of the dual-hose research-grade waterpipe (RWP); data acquisition system not shown.

*Figure A-6. The neck of the RWP was modified with a thicker upper lip and clamp to create a safer seal with the cap, given the manufacturer has reduced the flask's wall thickness.*

measurement and recording of the flow rate of smoke drawn through the hose. The two RWPs are connected to the same signal amplifier. This allows the separate measurement and reporting of two individual's puffing behaviors (puff volume, duration, flow rate, and interpuff interval) when each are smoking separate RWPs in separate, well-ventilated rooms in our controlled clinical research facility. The pneumotachometer introduces minimal draw resistance to the RWP (<5% at 27 L/min), and performs reliably, with known precision and accuracy, when measuring flows of waterpipe tobacco smoke. The relationship between pneumotachometer response and flow through the hose of each RWP is best described using a quadratic curve fit, as shown previously in Figure A-3.

being manufactured (by Kimax) with thinner walls, the neck could no longer safely support the old design. The new design includes a thicker mouth on the flask which supports the weight of the cap. The cap is now sealed to the top of the mouth of the flask using an o-ring and a clamp, as shown in Figure A-6. The dimensions and materials of the head, body, and one-way valve are unchanged from the original RWP.

#### Topography Data Collection and Analysis

Each RWP has an inline topography system that allows real-time

## Appendix B: COVID-19 Related Procedures

Due to the COVID-19 pandemic, processes and procedures have been implemented to help protect participants and research staff. These processes and procedures will be followed as long as social distancing requirements are necessary for conducting study visits.. All study participants will be provided with a facemask upon entry. The research assistant will meet the participant outside the building for a temperature check, direct the participant into the building, and the two of them will ride the elevator to the 4th floor physically distanced at least 6 feet apart, both wearing masks. No more than 2 persons may ride the elevator at any given time. The participant will immediately be escorted to a private exam/draw room. Therefore, there will be no waiting in open lobby/waiting areas.

When in the exam room, the research assistant will stand at least 6 feet away from the study participant to give instructions. Afterwards, the study coordinator will leave the exam room to allow the study participant to conduct the instructed procedures. The research assistant and study participant will be at least 6 feet away from one another and wearing protective masks at all times during each visit.

Each research assistant will have a designated exam/draw room and smoking room in which to conduct their designated research study. Each smoking room is separated from the staff control station in the hallway by its own door and contains a large window for the research assistant to be able to see in and monitor study participant activity within the room. There is also a speaker and microphone system within each smoking room along with the Genetec software system on the outside of each room at the computer stations. Therefore, the research assistant and study participant can communicate with one another without being in the room together.

For study measures which cannot be physically distanced, appropriate PPE will be worn at all times by research staff during these procedures including goggles, face masks, gloves, and isolation gowns or lab coats.

After each participant visit is complete, there will be at least a 45-minute period for cleaning and air exchange in the negative pressure rooms, and for cleaning exam rooms and equipment before the next participant visit. All smoking rooms are under negative pressure with a ventilation rate of 36.8 – 44.1 air changes per hour (ACH).

## Appendix C: Example Safe Departure Checklist

## [name]/[name], IRB 2018C0064, Evaluating Waterpipe Puffing Behaviors

Participant ID:    DYAD ID:  -   Date:  /  /   
Month Day Year

Visit #: \_\_\_\_\_

Visit Start:  :  Hour  :  Minute  AM or PM

Visit End:  :  Hour  :  Minute  AM or PM

Participant Height:  .  cm Participant Weight:  .  kilograms

### Safe Departure Checklist

#### Questions to assess safe departure from laboratory

At the end of the laboratory session, ask participant these questions and record the answers:

	Yes	No
1. Do you have a headache?		
2. Are you feeling any dizziness?		
3. Do you feel overly tired or fatigued?		
4. Are you feeling nauseous?		
5. Are you feeling light-headed?		
6. Do you feel mentally confused, disoriented, or like you are having trouble ordering your thoughts?		

If the answer to any of these questions is yes, ask the participant to remain seated. Offer the participant a snack and water, but do not force them to eat or drink. If you must leave the laboratory, make sure a study team member sits in the room with the participant, and notify the study PI, or the PI's designee if the PI is not available, as soon as safely possible.

If the participant requests to go to the bathroom, ask the participant to please remain seated until further assessment can be made prior to allowing them to stand unassisted.

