## I. Objectives

The study addresses the following FDA Scientific Interest Areas: Chemistry and Engineering, Toxicity, Behavior and Addiction; in that it will determine how specific WP tobacco additives affect users puffing behavior, liking, the quantities of toxicants they inhale and take up into their bodies, and acute pulmonary affects from WP tobacco smoking. These data will inform potential FDA product standards, or maximum limits for additives in WP tobacco, to curb the harm, addictiveness and appeal of WP tobacco smoking. Our multidisciplinary team includes experts in the conduct of clinical trials, WP smoking behavior, WP emissions testing, tobacco product analytical chemistry, psychophysical measurement, and tobacco use risk perception. In the research conducted at The Ohio State University (OSU), we will conduct the study according to the following aims. Note that Aim 3 is the only aim that involves the use of human participants.

Aim 1: Characterize select harmful and potentially harmful constituents (PHHCs) and sugar content of four WP tobaccos (one brand prepared four different ways to vary glycerol and sugars). A commercial WP tobacco brand will be modified to produce four different tobaccos:

- (1) Medium glycerol (60 mg/g), Medium sugars (350 mg/g)
- (2) High glycerol (120 mg/g), Medium sugars (350 mg/g)
- (3) Medium glycerol (60 mg/g), High sugars (510 mg/g)
- (4) High glycerol (120 mg/g), High sugars (510 mg/g)

Aim 2: Characterize select HPHCs and sugars yield in mainstream smoke generated from the four WP tobaccos characterized under Aim 1 using machine smoking of the research-grade waterpipe, and a standardized WP puffing regimen. Hypothesis: Mainstream smoke generated from WP tobacco with higher concentrations of glycerol and sugars will have higher concentrations of HPHCs.

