### II.3. How Can Sweet WP Tobacco Additives (Sugars and Glycerol) Contribute to Direct Harm?

WP tobacco smoking is associated with increased risk for lung, oral, esophageal, and head and neck cancers, and cardiovascular and pulmonary disease. Despite its growth in popularity over the past 30 years, there is little data available on the ingredients in WP tobacco, as the bulk of research has focused on toxicant yields in the smoke that is inhaled. WP tobacco is very different from cigarette or even pipe tobacco in that initial reports show that sweet tasting additives such as sugars and glycerol can comprise up to 70% of WP tobacco by weight.

Glycerol, which is not a sugar but still tastes sweet, can comprise 23–63% of the weight of the tobacco. Sugars such as sucrose, glucose, and fructose can also make up more than a third of WP tobacco weight. These same compounds are added to cigarettes, but at much lower levels (1-5%), to impart “smoothness” to the smoke and act as moisturizing agents, preservatives and solvents for flavor application. During the heating process, these sweet additives form volatile carbonyls, compounds that are known carcinogens and pulmonary toxicants such as acrolein, formaldehyde (IARC Group 1 carcinogen) and acetaldehyde (IARC Group 2B). During smoking, glycerol can dehydrate to acrolein; thus it is not surprising that, given WP tobacco is heavily fortified with glycerol, acrolein levels in WP smoke exceed those in cigarette smoke by a factor of 15 (see Table 3). Acrolein is ciliotoxic and can inhibit both the immune system and lung clearance. When heated, glycerol can also produce formaldehyde and acetaldehyde, which are both contributors to lung cancer in cigarette smokers and chronic obstructive pulmonary disease. Moreover, acetaldehyde increases the abuse liability of nicotine, contributing to the addictiveness of tobacco smoke. Short-term effects from exposure to these carbonyls results in pulmonary irritation and edema. After their authorities were extended to more novel tobacco products like WP, FDA proposed adding glycerol to the HPHC list.

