**Spirometry.** Before and after smoking at each clinic visit, subjects will be asked to take a deep breath and then instructed to exhale forcefully into a handheld spirometer [NDD EasyOne Air Spirometer (NDD Medical Technologies, Andover, MA), or similar spirometer] according to American Thoracic Society Guidelines. This maneuver will be repeated up to 5 times in order to

ensure reproducible results. This non-invasive procedure will take up to 15 minutes to perform. Participants' height and weight will also be measured to calculate their expected spirometry measures as thresholds to use for determining potential impairment in lung function.

Safe Departure and Remuneration. At the end of each clinic session, research assistants will assess each of the participants for safe departure using a standardized checklist. An example checklist is provided in Appendix C. Visits 2-4 will be similar to the first visit, but the tobacco and use history data collection and the urine pregnancy test (women only) will not be repeated. Participants will receive \$50 for each laboratory visit and a bonus payment of \$50 for completing all four visits, for a total of \$250 at the conclusion of the last laboratory visit.

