## V. Risks, Benefits, Safety Plans

### V.1. Risks associated with the human study

Potential risks are minimal for the human participant study. Potential risks associated with the procedures and equipment that will be used to collect the exhaled breath CO, topography, and pulmonary data are minimal. Potential risks resulting from collecting blood samples include being unable to provide blood samples because forearm veins are not adequate, feeling light-headed or faint, nausea, dizziness, hematoma or bruising at or near the needle site. We minimize this risk by using certified technicians with extensive experience in collecting blood samples. However, if the participant does not feel comfortable for any reason and wants to end their participation in the study, he/she can do so at any time without penalty. Some of the survey questions may upset individuals; however, we have used these questions and procedures in many previous studies without upsetting participants.

There are no potential risks involved in the collection of waterpipe smoking topography, as the device does not change the resistance to draw or toxicity of the smoke inhaled. The data are acquired continuously to an electronic file, and may be displayed on a laptop screen that is not viewable by either participant. Therefore the possibility of the participant amplifying their puffing rate in order to see the on-screen response is eliminated.

Participants may feel hungry because they will not be permitted to eat until after their post-smoking lung function test is completed. Pulmonary function studies involve forceful respiratory maneuvers and occasionally people develop light-headedness during the procedures or soreness of the chest for a few days. Subjects will be seated and closely monitored by trained/certified personnel during those procedures.

The RWP that participants will smoke at the clinic is specially designed for investigational research only, and as such may have unknown health risks. Both the single- and dual-hose versions of the RWP have been used by participants in several previous studies.

A potential risk is loss of confidentiality. We have rigid procedures in place to protect against loss of confidentiality. Participant identifiers will be kept in a locked file cabinet. This study is not unlike our previous work investigating the efficacy of WP warning labels; we collect the

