#### Instructions:

*The Safe Departure Checklist is a standard set of data entered for every subject that engaged in laboratory smoking prior to their departure from the lab.*

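### The example safe-departure checklist asks nothing about breathing, so on that form an isolated respiratory symptom would not trigger the remain-seated step

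*Combined protocol and SAP*

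**What the plan says.** Section IV, under Safe Departure and Remuneration, states that at the end of each clinic session "research assistants will assess each of the participants for safe departure using a standardized checklist". It then adds: "An example checklist is provided in Appendix C".

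The Appendix C form is headed "IRB 2018C0064, Evaluating Waterpipe Puffing Behaviors", which is not this protocol's title, and it carries a dyad ID field. Its six questions cover headache, dizziness, fatigue, nausea, light-headedness and mental confusion. The action text begins "If the answer to any of these questions is yes, ask the participant to remain seated". It goes on to offer a snack and water, and to restrict standing unassisted until a further assessment. A clause on notifying the PI or designee sits in a sentence about what to do if the staff member has to leave the room. The Instructions describe the checklist as a "standard set of data entered for every subject that engaged in laboratory smoking prior to their departure from the lab".

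On the hazard, Section II.3 says that glycerol and sugars form volatile carbonyls when heated, and continues: "Short-term effects from exposure to these carbonyls results in pulmonary irritation and edema". Section I lists "acute pulmonary affects from WP tobacco smoking" among the things the study will determine.

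**The concern.** The departure check is the last structured contact before a participant who has just smoked leaves the building. Its questions suit faintness, nausea and disorientation. They do not cover the organ system that the protocol itself identifies as the short-term target of the additives' combustion products. A participant with only new breathlessness, wheeze, chest tightness or cough would not be asked about it at that point, and nothing on the form would hold them back. What is at stake is participant safety at one step of the visit. No outcome, comparison or error rate depends on it.

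**Working it through.** The plan gives no figure to reproduce, so the check is a count and a comparison of texts.

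1. **Items on the form (Appendix C).** Headache, dizziness, fatigue, nausea, light-headedness, confusion: 6 items, of which 0 are respiratory. The numbering stops at 6 and the action text follows directly, so the question list appears complete.

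2. **Trigger.** The action needs a yes to a listed question. A participant with only a respiratory symptom gives 0 yes answers out of 6, so the remain-seated step is not reached. PI notification may apply only when staff must leave the room; on either reading it also requires a yes first.

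3. **Other places where a breathing problem could surface.**
   - *Spirometry (Section IV).* It is repeated after smoking at every visit, and expected values serve as thresholds for possible impairment. The protocol attaches no departure action to a result, and spirometry measures function without asking about symptoms.
   - *Staff observation (Section V.1).* "Subjects will be seated and closely monitored by trained/certified personnel during those procedures" That statement concerns the lung function procedures. Section IV places questionnaires after them and the departure check at the end of the session. Appendix B also describes observation of the smoking room by window and intercom.
   - *Adverse events (Appendix D).* Events are self-reported at follow-up visits and managed at once, and safety issues are discussed immediately with the PIs. No respiratory prompt is given. If a follow-up visit means the next session, it is at least a week later, and none is described after the fourth.
   - *Entry criteria (Table III.4).* Smoking-related disease and several recent respiratory conditions are excluded. The asthma item covers uncontrolled or worsening asthma, so that item does not exclude controlled asthma.

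   Each lowers the risk. None asks about breathing symptoms at departure or feeds the departure decision.

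4. **How often the form would be used, if it is this study's form.** With the target of 50 complete data sets: 50 × 4 = 200 sessions. With all 60 recruits completing: 60 × 4 = 240 sessions. The documents give no rate of respiratory symptoms after smoking, so no event count follows.

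**The case against.** The strongest objection is that the form is only an example. Section IV calls it one, and its heading belongs to another study. The checklist actually used may differ, so the 200 to 240 sessions are conditional on an assumption. That stands, and it limits the point to the form shown. It also gives the sponsor a simple answer if the real form is better. Text between the action paragraph and the Instructions in Appendix C was not available to me, so the form's full response procedure cannot be judged. The items of the subjective-effect scales named in Section III.C3 are not shown either.

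Second, the existing response of a seat, a snack and water does not suit a breathing complaint, so adding questions alone would achieve little. That is also right, and it shapes the fix.

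Third, the hazard statement is background and gives no dose or rate for one session. Participants are experienced users, and the study tobaccos contain 60 to 120 mg/g glycerol against 246 mg/g in the flavored commercial product (Table II.2). This supports a low priority, although the comparison does not extend to sugars: the high-sugar products total 90 + 195 + 225 = 510 mg/g against 0 + 195 + 190 = 385 mg/g.

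A reader might infer that the protocol has no respiratory safety monitoring, or that participants will leave with unrecognised lung injury. The documents support neither. Spirometry follows every smoking session, adverse events are assessed, entry is screened, and nothing in the plan allows harm to be counted. Nor can one say that every yes on the form leads to PI notification, and so that such notification is what the participant loses.

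**Conclusion.** The point holds in a narrow form. The only departure checklist shown has 0 respiratory questions out of 6, while the protocol names pulmonary irritation and edema as short-term effects of carbonyls from its own study additives. On that form an isolated breathing symptom would not trigger the remain-seated step, and no other safeguard described is linked to departure.

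The size is one missing prompt, in about 200 to 240 sessions if the example is the form in use. This rests on two assumptions: that the numbered list is complete as it appears, and that the study's own form matches the example. It is an optional, low-cost safety improvement.

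**What to change.** In the checklist used for this study, add one yes/no question: since smoking, has the participant had new or worsened shortness of breath, wheeze, chest tightness or persistent cough? State the response to a yes: the participant stays, staff look at the post-smoking spirometry already collected, and the PI or designee is notified before departure, whether or not staff need to leave the room. If the form in use already asks this, replace the Appendix C example with it.

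The cost of asking is small. At an assumed 0.5 to 2 minutes per session, it runs from 200 × 0.5 / 60 = 1.7 hours to 240 × 2 / 60 = 8.0 hours of staff time over the whole study, excluding time spent following up a yes. The downside is a few longer stays and extra notifications. Some will reflect chest soreness from the spirometry itself, which Section V.1 lists as a known effect.
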